2.0 Background

Non-metastatic rectal cancer has been treated with radiotherapy (RT) alone, surgery with adjuvant RT or Chemo-Radiotherapy (CRT), and neo-adjuvant RT or CRT followed by surgery. Reports of RT only for selected patients with early stage resectable rectal cancer yield 5-year survivals of 50-90%, with many deaths from intercurrent illness. RT only for locally advanced disease, usually external beam with a brachytherapy boost, for resectable rectal cancer is reserved for patients refusing surgery or with co-morbidities rendering them medically inoperable. Nevertheless, results are respectable, with 5-year survivals typically greater than $60\%^{2-5}$. Such data establishes RT alone as a curative modality.

For many years, it has been known that adjuvant RT reduces local recurrence in locally advanced rectal cancer⁶. Neo-adjuvant CRT has proven superior to adjuvant CRT in a randomised controlled trial, with reduced acute and long-term toxicity. Two recent randomised trials have demonstrated the efficacy of concomitant chemotherapy, and have established preoperative CRT as the standard of care for locally advanced rectal cancer. The European Organisation for Research and Treatment of Cancer has published preliminary and 5-year results of its EORTC 22921 trial, randomizing over 1000 patients with T3 or resectable T4 into a 2x2 factorial design: preoperative RT alone, preoperative CRT, preoperative RT with 4 cycles of adjuvant chemotherapy, or preoperative CRT with 4 cycles of adjuvant chemotherapy⁸. Chemotherapy was 5-FU (350mg/m²/day) and Leucovorin (20mg/m²/day) for all arms, on the first and last week during RT, or as 4 courses every 3 weeks adjuvantly. RT was 45Gy in 25 fractions over 5 weeks in all arms. Patients within the CRT arms had smaller tumours on pathological assessment (p<0.0001), and greater downstaging (p<0.001). pCR rate was 5.3% and 13.7% in RT and CRT arms respectively. 5-year results reveal a local control advantage (incidence of local recurrence as a first event) for the three chemotherapy arms (7.6-9.6%), compared to RT alone $(17.1\%, p=0.002)^9$.

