There has been growing interest in selecting those patients who are likely to achieve pCR. This is of particular importance for patients with low rectal cancers who would otherwise require an Abdomino-perineal resection. Whilst identification of these patients is impossible with a single scan, it is reasonable to adopt a policy of stringent monitoring with serial imaging, clinical examination and CEA, especially in individuals who refuse a stoma and those with significant comorbidities (high risk for surgery).

The same Brazilian group have reported the long-term results of a non-surgical approach for patients who have achieved a complete clinical and radiological response for chemo-radiotherapy¹⁴. 265 patients with distal resectable rectal tumours were treated with neo-Adjuvant CRT from 1991 to 2002. RT dose was 50.4 Gy in 1.8 Gy per fraction for 6 consecutive weeks. Patients received concurrent chemotherapy with 5FU (425 mg/m²) and Leucovorin (20 mg/m²) on the first and last 3 days of RT. Patients were assessed at 8 weeks following completion of CRT. 71 (26.8%) of patients were judged to have achieved CR on the basis of clinical and radiological grounds ('stage 0'), though MRI was not used. These patients did not have surgery. All other patients proceeded to surgery. 7% of those with incomplete clinical response (residual rectal ulcer) proceeded to surgery and proved to have a pathological complete response (pCR).

The mean follow-up period was 57.3 months (range 18-156 months). 5-year overall and disease-free survival rates were 88% and 83% in the resection group and 100% and 92% in the Observation group respectively. 10-year cancer related overall and disease-free survival rates were 100% and 86% respectively. Of 71 patients considered to be in stage 0 following CRT, 69% were T3, 11% T4, and only 22% radiologically staged as node positive. Apparently 20% of all patients were T2N0.

Of 71 patients who had achieved complete clinical and radiological response, only 2 suffered an endoluminal relapse, both of whom were successfully salvaged. 3 patients developed metastatic disease.

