3.0 STUDY OBJECTIVES

The primary objective of this study is to establish the time to maximum tumour response following CRT, and to investigate whether surgery can be safely avoided within the tight framework of the trial follow-up protocol in a small group of patients where the cancer becomes undetectable by imaging modalities.

It also allows the use of 18F-FDG PET/CT in combination with MRI and clinical examination (tri-modality assessment) to assess for a continued incremental response to CRT. It should be made clear that surgery is not withheld from patients entering this study. Indeed, surgery is an option at each stage of patient follow-up and is a crucial component of a patient's treatment pathway if a point is reached when there is no further regression of disease. However, should the patient refuse surgery or be medically unfit for a rectal surgery, they will continue to be followed up without surgical intervention. If a status of 'no detectable disease' by serial MRI, PET/CT and clinical assessment is achieved and the patient wishes not to have surgery, they will continue to be stringently monitored within the framework of the trial follow-up protocol.

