8.0 STATISTICAL CONSIDERATIONS

Analysis methods

All time-to-event endpoints will be measured from the end date of chemoradiotherapy, and calculated using Kaplan-Meier methods. The final analysis will be carried out when all patients have had at least 2 years follow-up. An additional overall survival analysis may be carried out after all patients have had at least 10 years follow-up. **Patients who have not yet experienced the event in question will be censored at date of last follow-up**.

Primary endpoints

Since all patients will have at least two years complete follow-up, the percentage of patients in continued response without surgery at two years, and the percentage of patients with local failure at two years, will be calculated as percentages of all patients, with exact 95% binomial confidence intervals.

Secondary endpoints

Time to distant disease will be measured as the time to the first diagnosis of lymph node or other distant disease, confirmed via PET/CT, MRI, CT or pathology.

Time to maximal tumour response will be defined as follows: for patients who achieve CR, it is the time until first recorded MRI scan with tumour grade T0. In patients where this has not happened, it will be the time to the first of two consecutive MRI scans which show the same modified Mandard regression grading (or the first of two consecutive scans in which the second scan shows an increased Mandard regression grade). Patients with a continuing reduction in Mandard grade at the time of analysis will be censored at the date of last scan..Patients who opt for surgery or withdraw for other reasons before recorded maximal response will be censored at date of last scan.

Time to local regrowth will be measured as the time until the first recorded increase in Mandard grade, on MRI. Patients with continued stable disease or complete response will be censored at date of last MRI scan. Patients who opt for surgery or withdraw for other reasons before recorded local regrowth will be censored at date of last scan.

Of all patients who had surgery for progression of local disease, the percentage with positive margins will be calculated, with an exact 95% confidence interval. The percentage who had negative margins and had their sphincters preserved will also be calculated with an exact 95% confidence interval

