Progression free survival will be measured as time until the first occurrence of any of the following: increased Mandard grade (in patients who did not achieve CR), any tumour T1 or above (in patients who achieved CR), first diagnosis of nodal or distant disease (diagnosed on MRI, CT, PET or pathology); or death from any cause.

Quality of life will be measured using EORTC QLQ-C30, IBDQ and Vaizey questionnaires. Missing data will not be replaced, but numbers assessed at each time-point will be reported. Change from baseline will be assessed at each time-point and summarised using descriptive statistics. In addition, counts and percentages of LENT-SOMA worst grades at each time-point will be reported.

Sample size

We wish to show that the percentage of patients who can successfully omit surgery is at least 10%, with a true rate expected to be at least 25% (and possibly this may be considerably higher). The two-year failure rate is assumed to be no more than 5%, and a failure rate of 15% or more would be considered to be unacceptable.

Using a single-stage exact phase II design, with one-sided significance level of 0.05, then a total of 59 patients would provide 80% power to prove a 2-year failure rate of less than 15% if the true rate is no more than 5%. The trial would be a success according to this endpoint if no more than 4 patients out of 59 have local failure at 2 years. The same number of patients would provide at least 90% power to show that the proportion of patients safely omitting surgery is more than 10%, if the true rate is

expected to be at least 25%. The trial would be a success according to this endpoint if at least 11 out of 59 patients have safely omitted surgery. To be judged a success overall the trial must pass both of these endpoints (no more than 4 patients with local failure, and at least 11 safely omitted surgery).

We expect to recruit 39 patients from the Royal Marsden and network hospitals and 20 patients from other multi-centre sites. This recruitment is expecting to be completed by 31st December 2012. We believe 60% of eligible patient will wish to participate in the "deferral of surgery". However, only 20% of rectal patients who undergo pre-operative CRT will develop a complete response and meet the inclusion criteria.

Stopping Rule

The trial will be stopped if 5 patients develop disease which is surgically not

salvageable or incompletely excised. There will be continuous monitoring of all

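### Kaplan-Meier with deaths censored can overstate the proportion developing distant disease; the cumulative incidence is the better estimate for this secondary endpoint

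*Protocol*

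**What the plan says.** Three statements in protocol section 8.0 settle how this endpoint is estimated.

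- The estimator, under Analysis methods: "All time-to-event endpoints will be measured from the end date of chemoradiotherapy, and calculated using Kaplan-Meier methods".
- The censoring rule, in the same paragraph: "Patients who have not yet experienced the event in question will be censored at date of last follow-up". No exception is made for death.
- The event, under Secondary endpoints: "Time to distant disease will be measured as the time to the first diagnosis of lymph node or other distant disease". Death is not included.

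Where death is meant to count, the protocol says so. The progression-free survival definition in 8.0 ends with "first diagnosis of nodal or distant disease (diagnosed on MRI, CT, PET or pathology); or death from any cause", and section 6.2 defines overall survival by death from any cause. The protocol mentions neither cumulative incidence nor competing risks.

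On who is followed, section 3.0 says that "should the patient refuse surgery or be medically unfit for a rectal surgery, they will continue to be followed up without surgical intervention". Section 4.1 admits WHO performance status up to 2. On timing, section 8.0 places the final analysis when every patient has at least two years of follow-up. The only later analysis it names is an optional one of overall survival at ten years.

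**The concern.** A patient who has died cannot later be diagnosed with distant disease. Censoring that patient makes Kaplan-Meier assume that the patient's later risk equals that of the patients still alive and under observation. One minus Kaplan-Meier then estimates the risk in a hypothetical setting where nobody dies of anything else first. It is not the share of the cohort that develops distant disease.

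Readers will want that share, because distant spread is one of the outcomes to weigh when surgery is deferred. There is also a mismatch of scale. The two primary endpoints are percentages of all patients, so a patient who dies without local failure stays in the denominator. A distant-disease figure from one minus Kaplan-Meier does not sit on the same footing.

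**Working it through.** **The plan's own figures.** The protocol states no number for time to distant disease, so there is none to reproduce for this endpoint. The design figures in 8.0 rest on the two primary endpoints and do reproduce with exact binomial probabilities. With at most 4 local failures in 59, the type I error at a 15% rate is 0.0469 and the power at 5% is 82.8% (stated: 80%). With at least 11 of 59 omitting surgery, the type I error at 10% is 0.0306 and the power at 25% is 90.3% (stated: at least 90%). Distant disease enters neither.

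**Direction of the bias.** Take 59 patients, one of whom dies free of distant disease before the first diagnosis, with no other censoring. At that diagnosis Kaplan-Meier adds 1/58 = 1.72%, because the dead patient has left the risk set. The true proportion is 1/59 = 1.69%. Every such death has this effect on every later diagnosis. One minus Kaplan-Meier is therefore never below the cumulative incidence, and equals it when no such death comes first.

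**Size.** Both rates below are assumptions; the documents give neither for this cohort. Let h1 be the constant hazard of distant disease and h2 that of death without distant disease.

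- One minus Kaplan-Meier, deaths censored: 1 - exp(-h1·t)
- Cumulative incidence: h1/(h1 + h2) × [1 - exp(-(h1 + h2)·t)]

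The death percentages are the two-year risks implied by h2 alone.

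Worked case at two years, with one minus Kaplan-Meier of 20% and deaths of 10%:

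- h1 = -ln(0.80)/2 = 0.1116 and h2 = -ln(0.90)/2 = 0.0527
- cumulative incidence = 0.1116/0.1643 × (1 - 0.80 × 0.90) = 0.679 × 0.28 = 19.0%
- overstatement = 20.0 - 19.0 = 1.0 point

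Cumulative incidence at two years, with the overstatement in points in brackets:

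| One minus KM | Deaths 2% | Deaths 5% | Deaths 10% | Deaths 15% |
|---|---|---|---|---|
| 10% | 9.9% (0.1) | 9.8% (0.2) | 9.5% (0.5) | 9.2% (0.8) |
| 20% | 19.8% (0.2) | 19.5% (0.5) | 19.0% (1.0) | 18.5% (1.5) |
| 30% | 29.7% (0.3) | 29.3% (0.7) | 28.6% (1.4) | 27.8% (2.2) |

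With no such deaths the overstatement is 0 in every row.

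**If the curve is read later.** Carrying the same hazards to five years gives 23.2% against 22.6% at the low end (0.6 points) and 59.0% against 49.9% at the high end (9.1 points). These show how the gap grows. The protocol schedules no estimate of distant disease at that time.

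**Set against sampling error.** With 12 of 59 patients (20%), the exact 95% interval runs from about 11% to 33%. The largest two-year overstatement in the table, 2.2 points, is 0.022 × 59 = 1.3 patients.

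**The case against.** **Deaths may be few.** A reader might infer that deaths will be numerous, because section 2.0 describes series "with many deaths from intercurrent illness" and section 3.0 keeps patients unfit for surgery under follow-up. The documents do not support that. The remark in 2.0 concerns radiotherapy alone in selected patients with early-stage disease. Section 3.0 gives no share of unfit patients. The closest series in the protocol, the 71 observed complete responders in section 2.4, had 100% overall survival at five years; with no deaths the bias is zero. That series may flatter this cohort, since the trial also admits partial responders. The text settles neither many deaths nor few.

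**A late bias of about 5 points.** A true incidence of 25% with 30% competing deaths gives a total hazard of -ln(0.45) = 0.799. Distant disease takes 25/55 of it, or 0.363, and 1 - exp(-0.363) = 30.4%. The arithmetic is right, but it belongs to no planned analysis. Early recruits will have more than two years of follow-up, yet the only late analysis named is of overall survival, which has no competing event.

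**It is a choice of estimand, and the SAP may deal with it.** Kaplan-Meier with deaths censored is a common cause-specific summary, and the protocol does not say that it will be read as an absolute risk. Censoring at death is also inferred from the general rule and the event definition, not spelled out. Both points are fair and limit the weight of the concern. They do not remove it, because the protocol itself fixes the estimator and the censoring rule.

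**Little depends on it.** The endpoint is secondary, progression-free survival already combines distant disease with death, and an overstatement of harm is the cautious direction. This stands.

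**Local regrowth.** The same argument might seem to extend to time to local regrowth, with resection as a competing event. There, section 8.0 explicitly censors patients who opt for surgery. Changing that would change the question asked, which is a trade-off and not a correction, so it is not part of this point.

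**Conclusion.** The concern holds as a minor one. By its general censoring rule and its event definition, section 8.0 censors patients who die without distant disease, and one minus Kaplan-Meier then overstates the proportion developing it whenever such deaths precede later diagnoses. The direction is a matter of mathematics. The size, about 0.1 to 2.2 points at two years, rests wholly on assumed constant hazards over the ranges shown and is small beside the sampling error with 59 patients. It would matter more only if the curve were reported well beyond two years.

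It should not be read as showing that the trial will materially misstate distant disease, or that the design is at risk. Sample size, decision thresholds and both primary analyses are untouched.

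**What to change.** In section 8.0, under Secondary endpoints, add a sentence that the cumulative incidence of distant disease will be estimated by the Aalen-Johansen method, with death without distant disease as a competing event. Keep Kaplan-Meier for progression-free and overall survival, and leave the rule for local regrowth as it stands.

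The cost is one sentence and an estimator slightly less familiar to some readers. No new data are needed, because dates of death are already required for overall survival. If the sponsor prefers to keep Kaplan-Meier here, the section should at least say that the curve is a cause-specific summary with deaths censored and not the absolute risk of distant disease.

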2 has been achieved (if stable disease is demonstrated for such a patient on 2 consecutive scans during this period, the patient will be referred for immediate surgery). More frequent MRI scanning will be performed at the discretion of the MDM. A modified Mandard Tumour Regression Grade has been used for reporting (please see appendix 10.2).

The timing, indication and interpretation of biopsies is viewed as critically important in the context of this trial. Blind biopsies are discouraged, ie if there is no abnormality on sigmoidoscopy/ colonoscopy, then we do not recommend biopsies directed at the mucosa once occupied by the tumour. Biopsies are discouraged unless: i) an area of residual disease is visualised at (and no earlier than) 3-month Sigmoidoscopy; ii) a clinically suspicious area develops/re-appears at Sigmoidoscopy/colonoscopy; iii) MR changes raise the suspicion of recurrence.

Patients with evidence of clinical or radiological local recurrence will be referred immediately by phone and fax to the surgical team for urgent biopsy. It is anticipated that such concerns will be brought to light by MR imaging, and thus will automatically be discussed at the Unit MDM. If there is a clinical suspicion of recurrence from a source other than MR, then an urgent MRI will be considered depending on date of previous imaging. All such cases will be discussed at the next available MDM. If urgent salvage surgery is recommended, a PET/CT scan will be performed routinely pre-op to outrule occult metastatic disease.

Subjects with metastatic disease detected during follow-up will be treated according to the Unit MDM recommendation.

Patients with evidence of clinical or radiological local recurrence must be treated at least as urgently as a primary rectal cancer by the surgical team.

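### Time to local regrowth counts only an MRI grade increase and censors at surgery, so a pathology-confirmed regrowth can be analysed as event-free, and Sections 6.1 and 8.0 define the endpoint differently

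*Protocol*

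**What the plan says.** Protocol Section 8.0 (Secondary endpoints) gives the event: "Time to local regrowth will be measured as the time until the first recorded increase in Mandard grade, on MRI". Two censoring rules follow. For patients without the event: "Patients with continued stable disease or complete response will be censored at date of last MRI scan". For those who leave earlier: "Patients who opt for surgery or withdraw for other reasons before recorded local regrowth will be censored at date of last scan". The estimator is set for the whole section: "All time-to-event endpoints will be measured from the end date of chemoradiotherapy, and calculated using Kaplan-Meier methods".

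Other parts of the protocol describe regrowth differently:

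- **Section 6.1** counts documentation of recurrence or regrowth, with no limit on modality. Its time origin is the end of CRT for patients with a sustained complete response and the start of CRT for the others.
- **Section 7.0** makes a suspicious area at sigmoidoscopy or colonoscopy a reason for biopsy, and refers clinical as well as radiological evidence of recurrence for urgent biopsy. On imaging it says: "If there is a clinical suspicion of recurrence from a source other than MR, then an urgent MRI will be considered", depending on when the last imaging was done.
- **Section 8.0, progression-free survival**, counts "any tumour T1 or above (in patients who achieved CR"), without tying this to MRI.
- **Sections 4.4 and 7.0** withdraw from the trial, or refer for immediate surgery, patients not yet at regression grade 1 or 2 whose disease is stable on two consecutive scans.

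**The concern.** The trial follows patients with MRI, PET/CT and clinical examination (Section 3.0), but this endpoint recognises only one of the three. A patient whose regrowth is seen at endoscopy, proven by biopsy and resected can have no recorded MRI grade increase. Under the stated rule that patient is censored at the last scan and contributes no regrowth event.

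The second difficulty is the censoring itself. Kaplan-Meier assumes that patients censored at surgery would have had the same later risk of regrowth as those who stay under observation. Patients operated on for stable disease leave because of their response, and after resection the tumour can no longer regrow. One minus Kaplan-Meier then does not estimate the proportion of patients who regrow.

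At stake is how the trial describes local regrowth under deferred surgery, and whether two analysts working from Sections 6.1 and 8.0 would obtain the same number.

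**Working it through.** **1. Follow one patient through the text.** A patient in complete response on MRI develops a suspicious area at sigmoidoscopy, biopsy shows tumour, no further MRI is done, and surgery follows.

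| Rule | Result for this patient |
|---|---|
| 6.1 | Event (documented regrowth) |
| 8.0, time to local regrowth | Censored at last scan |
| 8.0, progression-free survival | Event (tumour T1 or above after CR) |
| 3.1, primary endpoint 1 | Not a success (had surgery) |

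The regrowth endpoint is the only one that treats this patient as event-free. For a patient who never reached CR, the local component of progression-free survival is again an increase in Mandard grade, so the contrast with that endpoint does not apply.

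**2. Time origin.** For patients without sustained CR, Section 6.1 starts at the start of CRT and Section 8.0 at the end. The two times differ by the whole duration of CRT.

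**3. The plan's own figures.** The protocol states no figure for this endpoint. The design figures reproduce by exact binomial calculation with n = 59:

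- Local failure, success if at most 4: P(X ≤ 4 | 0.15) = 0.0469 and P(X ≤ 4 | 0.05) = 0.828.
- Surgery omitted, success if at least 11: P(X ≥ 11 | 0.10) = 0.0306 and P(X ≥ 11 | 0.25) = 0.903.

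Neither uses time to local regrowth.

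**4. Illustration of size.** All rates here are assumptions; the protocol gives none. Let R be the true two-year cumulative incidence of regrowth, S that of surgery without regrowth, and e the share of regrowths that never show an MRI grade increase and are censored. With constant cause-specific hazards:

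- total cumulative hazard H = −ln(1 − R − S)
- regrowth part H_R = H × R/(R + S)
- planned estimate = 1 − exp(−H_R × (1 − e))

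*Missed events only* (R = 0.30, S = 0, e = 0.25): H_R = −ln 0.70 = 0.357; 0.357 × 0.75 = 0.268; 1 − exp(−0.268) = **23.5%**. With e = 0.10 it is 27.5%; with e = 0.50, 16.3%.

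*Censoring at surgery only* (R = 0.30, S = 0.20, e = 0): H = −ln 0.50 = 0.693; H_R = 0.693 × 0.6 = 0.416; 1 − exp(−0.416) = **34.0%**. With S = 0.10 it is 31.8%; with S = 0.30, 36.8%.

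*Both* (R = 0.30, S = 0.20, e = 0.25): 0.416 × 0.75 = 0.312; 1 − exp(−0.312) = **26.8%**.

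*Range for R from 20% to 40%*: e = 0.25 alone gives 15.4% to 31.8%; S = 0.20 alone gives 22.5% to 45.7%.

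Under these assumptions, counting regrowth from every modality and estimating cumulative incidence returns R in each case.

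**The case against.** Much can be said for the plan, and several stronger readings fail.

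- **Few regrowths may be missed.** Section 7.0 expects such concerns to come to light on MRI and allows an urgent MRI after other suspicion. This stands as a limit on size. It does not repair the rule, because the MRI is not required and a biopsy result is never an event.
- **The background series does not show that luminal relapse escapes MRI.** A reader might infer this from Section 2.4, where of 71 complete responders "only 2 suffered an endoluminal relapse, both of whom were successfully salvaged". MRI was not used in that series, so it says nothing about what MRI would have shown.
- **Operated patients are not kept in the risk set.** Censoring removes them. The fault lies in the assumption about their later risk.
- **The direction is not known.** A reader might conclude that regrowth will be understated. Missed events lower the estimate, while censoring at surgery raises it above the cumulative incidence. If operated patients had a higher underlying risk, even the estimate of regrowth in the absence of surgery would be too low.
- **The stable-disease rule may reach few patients.** Section 4.0 asks for no viable disease or grade 2 by week 8, although criterion (g) in Section 4.1 is looser. No rate can be taken from the text.
- **Censoring at surgery can be a deliberate target**: regrowth while surgery is deferred. That is legitimate as a secondary analysis, but the protocol does not say it is intended, and the informative censoring would remain.
- **Sampling error is larger.** At 30% with n = 59, the 95% half-width is 1.96 × √(0.3 × 0.7/59) = 11.7 points, against shifts of 6.5 and 4.0 points above. This limits the urgency, not the correctness of the point.
- **Pelvic nodes are a separate matter.** Section 8.0 says "Time to distant disease will be measured as the time to the first diagnosis of lymph node or other distant disease". A reader might infer that mesorectal nodal regrowth is misfiled as distant. That concerns another endpoint, and how to classify such nodes is a choice that the protocol's text does not show to be wrong.

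**Conclusion.** The point holds in limited form. The stated event rule can censor a pathology-confirmed local regrowth as event-free, and it conflicts with Section 6.1 on both the event and the time origin. Censoring at surgery depends on response status for patients referred with stable disease, so one minus Kaplan-Meier should not be read as the proportion who regrow. These conclusions rest on the text alone.

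The size rests on assumed rates: with 30% true regrowth, about 23.5% if a quarter is missed by MRI, about 34% if a fifth have surgery without regrowth, and 26.8% with both. The net bias cannot be signed from the protocol. The endpoint is secondary and carries no decision rule. The primary endpoints are percentages of all patients, and neither they nor the sample size of 59 change. The correction should be made, but the trial's success criteria do not depend on it.

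**What to change.** - **One definition, one origin.** Use the same text in Sections 6.1 and 8.0, timed from the end of CRT for all patients.
- **Event.** The earliest of (i) an increase in Mandard grade on MRI, or (ii) local regrowth found by endoscopy, DRE or PET/CT and confirmed by biopsy, by the resection specimen or by the review panel. State that residual tumour in the specimen of a patient operated on for stable disease, without suspected regrowth, is not regrowth.
- **Estimator.** Report cumulative incidence with surgery without regrowth and death as competing events. Keep the Kaplan-Meier analysis as a sensitivity analysis, described as regrowth while surgery is deferred.

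Cost: a change of wording and a little extra analysis, with no change to patient management. The reported event count may rise. Sections 5.4 and 7.0 already provide for central PET/CT review and for DRE and sigmoidoscopy forms. Section 6.6 promises the date of surgery only in the event of regrowth, so the date must also be recorded for surgery without regrowth. The forms are not in the text at hand, so whether biopsy results are captured on them should be checked.

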3.2 Secondary endpoints

- 1) Time to distant disease
- 2) Time to maximal tumour response after CRT
- 3) Time to local re-growth
- 4) Percentages of positive margins, and sphincter-preservation rates in patients who have had surgery.
- 5) Progression-free and overall survival
- 6) Quality of Life including long-term bowel, urinary and sexual function

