6.6 Rectal surgery

The date of rectal surgery will be documented in the event of tumour regrowth. The type of rectal surgery will also be documented (sphincter sparing vs APER). The margin status of the resected specimen will be analysed.

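### Section 8.0 computes margins only after surgery for progression and sphincter preservation only as a composite, whereas the endpoint in section 3.2 covers every operated patient

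*Protocol*

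**What the plan says.** Section 3.2, item 4, lists the endpoint as "Percentages of positive margins, and sphincter-preservation rates in patients who have had surgery". It sets no condition on why the operation was done.

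Section 8.0, under secondary endpoints, starts from a smaller group: "Of all patients who had surgery for progression of local disease, the percentage with positive margins will be calculated". The next sentence reads: "The percentage who had negative margins and had their sphincters preserved will also be calculated with an exact 95% confidence interval". That sentence names no denominator of its own, so it takes the one just given.

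Section 6.6 says: "The date of rectal surgery will be documented in the event of tumour regrowth". It goes on to say that the type of operation will be recorded and the margin status analysed.

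Elsewhere the protocol describes surgery that does not follow progression. Section 7.0, on patients who have not reached regression grade 1 or 2, says: "if stable disease is demonstrated for such a patient on 2 consecutive scans during this period, the patient will be referred for immediate surgery". Section 3.0 treats surgery as an option throughout follow-up and as essential "if a point is reached when there is no further regression of disease". Section 4.4(a) allows for a patient who decides to leave the trial and have surgery.

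**The concern.** The endpoint and its analysis describe different patients. Following section 8.0 to the letter would not produce what section 3.2 promises. There are two separate gaps:

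- **Denominator.** Patients operated on without progression are missing from the margin percentage and, by inheritance, from the sphincter percentage.
- **Quantity.** A sphincter-preservation rate is promised, but what is calculated is the share with both a clear margin and a preserved sphincter. A patient with a preserved sphincter and a positive margin counts as a failure in the composite and as a success in the plain rate.

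In a trial of deferred surgery, the results of the operations that do take place are a direct measure of what waiting costs. A rate restricted to one reason for surgery, itself an event after entry, answers a narrower question than the endpoint states.

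**Working it through.** **1. The trial's stated design.** This endpoint carries no sample-size figure. The design figures reproduce and do not depend on it. With X the number of patients out of 59:

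- Local failure, success if X ≤ 4: P(X ≤ 4 | 15%) = 0.0469 and P(X ≤ 4 | 5%) = 0.828, against the stated 0.05 and 80%.
- Surgery safely omitted, success if X ≥ 11: P(X ≥ 11 | 10%) = 0.0306 and P(X ≥ 11 | 25%) = 0.903, against the stated 0.05 and at least 90%.

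Section 8.0 takes both primary percentages over all patients.

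**2. Does surgery for progression cover the other routes?** Section 8.0's own definitions say it does not.

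| Route to surgery | Where | Treatment in section 8.0 |
|---|---|---|
| Stable disease on two consecutive scans, grade 1 or 2 not reached | 4.4(b), 7.0 | Continued stable disease is censored for regrowth |
| No further regression | 3.0 | An unchanged grade is neither regrowth nor a progression-free survival event |
| Patient choice | 4.4(a), 3.0 | Surgery before recorded regrowth is censored for regrowth |

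Progression-free survival needs a higher grade, tumour T1 or above after complete response, nodal or distant disease, or death. None of the three routes is such an event. No other section analyses margins or sphincter outcome for these operations.

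**3. How many operations?** The documents do not say. At the planning rate of 25% for safe omission, 0.75 × 59 = 44.25, so about 44 patients would not be in complete response without surgery at two years. At that rate, 44 is a ceiling on the number operated on by then, not an estimate. How many have surgery, and why, is not given.

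**4. Precision, with assumed counts.** The exact (Clopper-Pearson) 95% interval for x of n has lower limit Beta⁻¹(0.025; x, n − x + 1) and upper limit Beta⁻¹(0.975; x + 1, n − x). Assume 30 operations, half of them for progression, and the same positive-margin rate in both halves:

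- Progression only: 2/15 = 13.3%, interval 1.7% to 40.5%.
- All operations: 4/30 = 13.3%, interval 3.8% to 30.7%.

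Because the rate is held equal, this shows lost precision and nothing about bias.

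**5. Can the rate itself move?** With x₁/n₁ for progression operations and x₂/n₂ for the others, the overall rate is (x₁ + x₂)/(n₁ + n₂). It lies above x₁/n₁ only if x₂/n₂ does. Assume 2 positive margins in 10 progression operations (20%, interval 2.5% to 55.6%) and 10 other operations:

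- 0 positive among the others: 2/20 = 10% (1.2% to 31.7%).
- 1 positive: 3/20 = 15% (3.2% to 37.9%).
- 3 positive: 5/20 = 25%.

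The shift can go either way, and the documents give nothing to choose between these cases.

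**The case against.** **Salvage after progression is a coherent target.** Section 4.4 classes both surgery by patient decision and stable disease before grade 1 or 2 as treatment withdrawal, which may explain the narrower set. Rewording section 3.2 would also remove the contradiction. That is true as a matter of form. But section 3.2 makes no such exclusion, and narrowing it would leave the other operations unreported.

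**The stable-disease group may be small.** Referral under section 7.0 applies only before grade 1 or 2 is reached, and section 4.0 largely admits patients already at that level by week 8. Only the looser wording of 4.1(g) leaves more room. This stands. The other routes, lack of further regression and patient choice, remain.

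**The plain sphincter rate can be derived.** Section 6.6 records whether the operation was sphincter-sparing. That also stands, but section 8.0 does not plan to report the rate.

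**A reader might infer that primary endpoint 1 cannot be evaluated** because section 6.6 ties the surgery date to regrowth. The documents do not support this. The endpoint needs surgery status at two years. Section 7.0 requires a proforma at every visit, and the censoring rules in section 8.0 presuppose that surgery without regrowth is known. Section 6.6 is incompletely worded; it does not say that other operations go unrecorded.

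**A reader might also infer that these patients vanish from the trial's assessment.** They do not. They stay in both primary denominators, and the stopping rule counts incompletely excised disease whatever the reason for surgery.

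**Conclusion.** The contradiction between sections 3.2 and 8.0 stands in the current text. As written, the analysis omits operations done without progression and never gives the plain sphincter-preservation rate. The consequence is confined to one descriptive secondary endpoint; the primary endpoints, N = 59, the success rules and the stopping rule are unaffected.

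The size cannot be computed from the documents. The intervals of 1.7-40.5% and 3.8-30.7% rest on an assumed 30 operations, half of them for progression, at one common rate. A reader might infer that section 8.0 flatters deferral by leaving out poor surgical results. The documents do not support that, because the rate in the omitted operations could be higher or lower. The change is worth making because the plan would otherwise not deliver its stated endpoint, and correcting it costs little.

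**What to change.** 1. In section 8.0, set the denominator for margins to all patients who have rectal surgery for any reason. Show the result overall and by reason (regrowth or progression, stable disease or no further regression, patient choice), with surgery for progression as a labelled subgroup. Keep the exact 95% intervals.
2. In section 8.0, report plain sphincter preservation in all operated patients, with the negative-margin composite as an additional line.
3. In section 6.6, state that date, type and margin status are documented for every rectal operation, and add the reason for surgery.

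No clinical rule changes and no sample size is affected. The cost is the wording, one data item for the reason, and the operation and pathology reports that routine care already produces. For patients who leave the trial to have surgery, those reports can be used only as far as their consent allows, so the number missing should be stated. The progression-only result is kept as a subgroup, so nothing now planned is lost.
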